## Preliminary Data

Our group has conducted several prior studies to support the feasibility of the current proposal. The results of these studies are discussed as follows:

### 1) rTMS for neuropathic pain and MTBI-HA

In a collaborative meta-analysis study [39] from six major multinational TMS research centers with pooled individual data (n=149) from 5 published clinical trials, we were able to reveal the overall treatment effect of rTMS in neuropathic pain states. The result of the analysis strongly suggests that the analgesic efficacy of multiple sessions of rTMS is more superior to a single session of rTMS as the overall treatment effect for the multiple session study is 20.4 % significantly (P=0.003) better than the overall effect of the single treatment session studies. The analysis also demonstrates the effect of rTMS on neuropathic pain consists of a differential "top-down" pattern based on the neuroanatomical origins of the neuropathic pain pathophysiology with centrally originated pain states such as post-stroke central pain syndrome as the top responders (**see below for excerpted study result figures**) to motor cortex rTMS. Like the post-stroke central pain patients, MTBI patients are known to demonstrate central diffuse neuronal injury, which makes them the ideal candidates for the treatment.

[figure not shown]

**Figure 3. Diagnosis and treatment effect.** Mean difference (95% confidence interval) in percent of pain visual analog scale (VAS) score change.\*P value is from Wald test for the interaction effect of diagnosis and treatment on the percent decrease in VAS score. This P value increases to 0.140 when we exclude the Khedr study. NR, nerve root; PN, peripheral nerve; PSP, post-stroke supraspinal related pain; TGN, trigeminal nerve or ganglion.

## 2) rTMS at the LMC in reducing MTBI-HA

In our recently published study, MTBI-HA subjects were randomized to receive three sessions of either real (N=12) or sham (N=12) rTMS at the left motor cortex with brain MRI neuronavigation guidance. Subjects received the real rTMS demonstrated a significantly higher degree of headache relief up to one month in the comparison to the sham group (see below for excerpted figures 3a and 3b from Appendix #6a) [44]. This observed headache relief efficacy with a relatively short duration of treatment sessions warrants further studies assessing the long-term benefit of rTMS in MTBI-HA management with a more robust and longer duration of treatment sessions.

[name] ET AL.

**Figure 3.** Change of persistent headache. a. Intensity of persistent headache in numerical rating scale (NRS), #  $p = 0.06$ . b. Percentage of reduction in persistent headache,\* $p < 0.05$ . Post\_WK1: posttreatment one week; Post\_WK4: posttreatment four weeks.

## 3) Prospective Case Series demonstrating the feasibility of rTMS in long-term management of MTBI-HA

[figure not shown]
Our internal prospective follow-up survey in over 150 patients and recently published case series supports the feasibility of using rTMS as a long-term therapeutic tool for MTBI-HA and migraine headache management [41; 81]. A well powered sample size and controlled study with a longer duration of treatment is warranted.

## 4) Supraspinal Functional deficit in patients with MTI-HA

[figure not shown]
Our published studies with functional magnetic resonance imaging (fMRI) suggest that patients with persistent MTBI-HA have significant

compromised medial prefrontal modulatory response to heat pain stimuli and their resting state medial prefrontal cortical connectivities to other pain related regions are diminished in comparison to age and gender matched healthy controls (**See excerpted study figures 3&4 from appendix #6b**) [44].

]. Although a previous study suggested blast-related traumatic brain injury (TBI) appeared to have a unique effect on brain function associated with cognitive inhibitory tasks that could be distinguished from TBI resulting from non-blast (blunt or motor vehicle injury) related TBI [17], our preliminary assessment with experimental heat pain stimulation found no significant difference in supraspinal modulatory response to experiment heat pain between blast (n=7) and non-blast Veterans (N=7) ([name] et al., unpublished data). When turning our attention to assess the headache severity related supraspinal pain modulatory functions, we found Veterans with **Mild** ( $\leq 1$  4 on a 0-10 NRS, numerical pain rating scale) intensity of headache appeared to have higher level of left medial prefrontal cortical function in comparison to their counterparts with **Moderate-to-Severe ( $\geq 5$  on 0-10 NRS)** head ache intensity in their response to heat pain stimulation under functional magnetic resonance imaging (fMRI). Therefore further mechanistic exploration is required to understand the potential impact of injury mechanisms and headache severities on the treatment outcome.

**Figure 3.** Resting state functional connectivity difference with the left medial prefrontal cortex (seeded region) of the Healthy Controls ( $N = 15$ ) demonstrating more significant ( $P < 0.01$ ) functional connectivity to the left secondary somatosensory cortex (SSC2) and right inferior parietal lobe (IPL) than patients with mild traumatic brain injury ( $N = 15$ ).

**Figure 4.** Resting state functional connectivity difference with the right anterior cingulate cortex (seeded region) of the healthy controls ( $N = 15$ ) demonstrating less significant ( $P < 0.01$ ) functional connectivities to the right secondary somatosensory cortex (SSC2) and inferior parietal lobe (IPL) than patients with mild traumatic brain injury ( $N = 15$ ).

### Section 9 - Design and Methods

9) Describe the research design and the procedures to be used to accomplish the specific aims of the project. Provide a precise description of the planned data collection (include what systems or databases will be used/accessed to gather data), analysis and interpretation. For chart review studies, include the timeframe of collection. Address sample size, inclusion of women and minorities. Define in clear terms exactly what will be done to the human subjects.

#### Research Design:

A total of 200 will be consented and 128 (64 per group, accounted for 36% dropout rate) patients will be randomized to be stratified based on their injury mechanisms (blast, non-blast) and headache severities (mild, moderate, severe) and enrolled over 6 years from VASDHS, and Naval Medical Center San Diego (MNCS). Patients meeting study enrollment criteria will be randomized into one of the two study groups (A&B) based on their mechanisms of injury, gender, severity of headache, and past failed therapies for their headache. The overall study duration for each subject is about 14 weeks developed into three phases according to the following schedule:

- 1) PRE-TREATMENT PHASE (weeks 1-2) consists of Visit 1 (Screening Visit) and Visit 2 (Pre-treatment Assessments);
- 2) TREATMENT PHASE (week 3-4) consists of Visits 3-12 (Neuronavigation guided rTMS consisting of 10 weekday treatments at  $>24$  and  $< 72$  hours apart, weekends excluded, maximum 5 weeks for treatment completion) rTMS will take place in Building 23 Room 105 at the VASDHS; and

3) POST-TREATMENT PHASE (week 5-14) consists of two initial weekly visits (Visits 13&14) and two additional biweekly visits (Visits 15&16) and one monthly visit (Visit 17).

Brain anatomical and functional MRI will be performed within 72 hours after Visits 2 and 13. Subjects will be required to fill out headache diary between assessment visits. Headache assessments along with quality of life, mood and functions assessments will be carried out at Visits 1,2, and 13--17. This frequency of treatment and duration of follow-up is in line with recently published rTMS articles related to TBI, headache and pain, and also in accordance with the 3-month post treatment initiation follow-up guideline /recommendation [32; 55; 80].

#### **A) Headache assessment (specific aim #1, see Appendix 6b for assessment samples)**

Due to the persistent and debilitating nature of MTBI-HA, two areas of headache characteristics: **1) Persistent Daily Headache**; and **2) Debilitating Headache Exacerbation** will be especially assessed during the study in addition to more conventional headache assessments. Patients will be provided with a daily headache diary, which they will fill out every evening during the study between-visit periods (B1-B6). In the diary, they will report if they have a persistent (non-stop, 24/7) headache over the last 24 hours and rate the average intensity of the headache on a 0-10 Numerical Rating Scale (NRS). In addition, they will be asked to report the duration and intensity of any debilitating headache exacerbations, which completely incapacitate their daily functions.

For persistent headache, the intensity of the headache from the diary will be averaged (sum of headache NRS scores/number of days) as between-visit persistent headache severity assessment. Should the headache becomes sporadic after the study rTMS interventions, the subjects will then record the total number hours of headaches over the previous 24 hours and the average intensity of the headache, they will still record the duration and intensity of any debilitating headaches. The occurrence of lingering persistent daily headaches and average intensity of daily headaches will be recorded [38; 43].

For debilitating headache exacerbation, a composite score will be generated by multiplying the average duration (hours/episode) of the headache exacerbation by the average frequency (episodes per day) and the average intensity (NRS) of the headache exacerbation [38; 45] .

Aside from assessing the daily intensity and exacerbation pattern of MTBI-HA, additional assessments for the impact of headaches on the patients' quality of life will include:

1) the **Headache Impact Test (HIT-6)** which will assess the impact of headaches on the subjects' ability to function on the job, at school, at home and in social situations [66; 79];

2) **Neurobehavioral Symptom Inventory (NSI) assessment** which will assess the pattern of headaches and other co-morbid neurological symptoms in Visits 2, 13, 14, 15, 16 & 17 [31; 60]. As a fail-safe assessment for any missing data, subjects will also be asked to rate the average intensity of headache in Visits 2, 13, 14, 15, 16 and 17 for the prior between-visit durations on a 0-100 Mechanical Visual Analogue Scale (M-VAS) [64].

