## Section 6 - Specific Aims

### 6) Provide a statement of specific aims and hypotheses that serve as the basis for this protocol. Emphasize those aspects that justify the use of human subjects.

1) Compare the long term treatment effect of active rTMS (Group A) to sham LMC rTMS (Group B) in reducing the intensity, frequency and duration of MTBI-HA and the overall analgesic usage;

Hypothesis #1: Active rTMS at LMC provides significantly more reduction in headache intensity, duration and frequency of exacerbation than sham rTMS;

2) Compare the long term treatment effects of Group A to Groups B in improving quality of life, mood and functions in patients with MTBI-HA;

Hypothesis #2: Active rTMS at LMC provides significantly more improvement in quality of life, mood and functions than sham LMC stimulations;

Coinciding with the specific aims, the proposal also consists of the following exploratory aims:

1) Explore the treatment effect on resting state supraspinal functional connectivity in the pain related network;

2) Explore moderators' effect of injury mechanisms (blast and non-blast) and the headache severity on the treatment .

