For hypotheses 1 and 2, where multiple analyses are conducted, correction for family-wise Type I error rates will be made using the Westfall-Young randomization maxTprocedure, which adjusts p-values for significance while taking into account the correlation of the outcomes [76]. In this way, the study can control for an overall family-wise error rate of .05 while achieving more power than Bonferroni adjustments. Using this method of power analysis, the investigators estimated a sample size of 128 (64 per group, accounted for a 20% dropout rate) provides the study with 85% power

to detect a medium effect size (RMASS program provided by Hedeker) [25; 26]. Medium effect sizes were used based on the results included in the above sections. Medium effect size is defined as a between-group difference increasing linearly from 0 at baseline to .5 SD units at the last time point. The minimum power estimation is based on sample size calculation for 10% and 20% attrition, correlations of 0.2, 0.5, and 0.8 between the repeated measures, and for medium and large effect sizes. Data will be analyzed using SPSS version 23, all analyses will be two-tailed, where applicable with  $\alpha = .05$ .

**Hypothesis #1:** Active rTMS at LMC provides significantly more reduction in headache intensity, duration and frequency of exacerbation than sham rTMS.

Independent Variables: Treatment Groups with two levels (Groups A & B), Visits up to 8 (See below). Dependent Variables: Primary outcome: Average daily headache assessments (B1, B2, B3, B4, B5, B6); Secondary outcome: Debilitating Headache Composite Score (B1, B2, B3, B4, B5, B6); M-VAS Scores of headache (Visits 2, 7, 12, 13, 14, 15, 16, 17); HTL-6 and NSI (Visits 2,13,14,15, 16, 17); headache rescue medication usage (Visits 2,13, 14, 15,16, 17). Note, not all variables are collected at all visits.

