## Section 9.8 Questionnaires & Surveys

**9.8) Provide the name and a reference for questionnaires/surveys that are standard or identify them here and attach a copy of the questionnaire/survey. Questionnaires or surveys that are not clinical standard references must be uploaded. Reference the help link for additional information related to surveys administered to VA personnel and approved platforms for web-based surveys.**

Questionnaires & Surveys (copies attached):

- 1.Numerical Pain Rating Scale (NPRS): scale that ranges from no pain to worst possible pain.
- 2.Headache Log: Daily log to report if they have a persistent (non-stop, 24/7) headache over the last 24 hours and rate the average intensity of the headache on a 0-10 Numerical Rating Scale (NRS). In addition, they will be asked to report the duration and intensity of any debilitating headache exacerbations, which completely incapacitate their daily functions.
- 3.Neurobehavioral Symptoms Inventory (NSI): A self-report on the severity of each symptom is measured using a 5-item scale. It asks the subjects to indicate the extent to which each symptom has disturbed them.
- 4.Headache Impact Test (HIT-6): Measures how impact headaches affect the individual's ability to function in different domains.
- 5.Short Form Health Survey-36: A patient-reported survey of patient health. It is a measure of health status and quality of life in regards to eight main areas: vitality, physical functioning, bodily pain, health perceptions, physical, emotional, and social role functioning and mental health.
- 6.Clinician-Administered PTSD Scale (CAPS-5): A 30-item structured interview that can be used to diagnose PTSD and associated symptoms.
- 7.Conner's Continuous Performance Test (CPT II): A widely used test of sustained attention using a computer program. It provides a detailed picture of response time, impulsivity, and attentiveness.
- 8.Hopkins Verbal Learning Test: Hopkins Verbal Learning Test: This is a verbal list learning measure with multiple equivalent forms to minimize practice effects in repeat testing. It provides information about learning acquisition as well as short and long delayed recall. It has been used successfully in previous trials of rTMS.

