### Additional Inclusion Criteria:

1. male or female age between 18 to 65;
2. no prior experience of TMS treatment;
3. average persistent headache intensity more than 30 on the 0-100 mechanical visual analog scale(M-VAS) at the screening visit (visit 1)[64] and average persistent headache intensity score greater than 3/10 on a numerical rating scale (NRS) reported in the headache diary (between visits 1&2);
4. no history of daily persistent headache prior to the MTBI incidence:

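### Does the primary daily headache score need a written rule for sporadic and headache-free diary days, and an outcome for headache hours?

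*Combined protocol and SAP*

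**What the plan says.** Section 9, part A (Headache assessment) of the combined protocol and SAP describes a diary completed each evening with a 0-10 NRS. Its scoring sentence reads: "For persistent headache, the intensity of the headache from the diary will be averaged (sum of headache NRS scores/number of days". If headache later becomes intermittent, "the subjects will then record the total number hours of headaches over the previous 24 hours and the average intensity of the headache", and the paragraph closes with "The occurrence of lingering persistent daily headaches and average intensity of daily headaches will be recorded". Debilitating exacerbations have their own composite, formed by "multiplying the average duration (hours/episode) of the headache exacerbation by the average frequency (episodes per day" and by average intensity.

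Under Data Management, Analysis and Power Calculations, the Hypothesis #1 list gives "Primary outcome: Average daily headache assessments (B1, B2, B3, B4, B5, B6" without a formula. The secondary outcomes are the debilitating composite, M-VAS, the headache impact test, NSI and rescue medication use.

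Three other places bear on the point:

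- Section 6, Aim 1, speaks of "reducing the intensity, frequency and duration of MTBI-HA and the overall analgesic usage".
- Section 9.8 describes the headache log as a "Daily log to report if they have a persistent (non-stop, 24/7) headache over the last 24 hours and rate the average intensity" and does not mention headache hours.
- The Additional Inclusion Criteria require "average persistent headache intensity score greater than 3/10 on a numerical rating scale (NRS) reported in the headache diary".

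**The concern.** Patients enter with persistent headache, so sporadic and headache-free days should arise mainly after treatment and more often in whichever arm improves. The formula is worded for persistent headache only. Taken literally, the days that show benefit have no stated place in the primary score. Three treatments are conceivable: count a free day as 0, leave it out of the denominator, or use persistent days only. They can give very different values for the same diary.

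Two further points add weight. The randomization section describes the study biostatistician as not blinded, and the blinding section sends all data straight to the biostatistician, so an open rule could be settled with treatment arm known. Aim 1 also names headache duration, yet ordinary headache hours are recorded with no stated use. If the diary item means intensity while headache is present, a large fall in hours at constant intensity would not move the primary score.

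**Working it through.** The plan gives no figure to reproduce on this point. Its 85% power for 64 per group does not depend on the scoring of free days. The diary values below are assumed, because the documents give no frequency of free days.

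**1. How far the divisors can differ.** Take 7 completed days with NRS 5 on each headache day.

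| Free days | Free days dropped | Free days = 0 | Gap |
|---|---|---|---|
| 1 | 6×5/6 = 5.0 | 6×5/7 = 4.29 | 0.71 |
| 2 | 5×5/5 = 5.0 | 5×5/7 = 3.57 | 1.43 |
| 3 | 4×5/4 = 5.0 | 4×5/7 = 2.86 | 2.14 |

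The order of two patients can reverse. Patient X, 7 days at NRS 4, scores 7×4/7 = 4.0 either way. Patient Y, 2 days at NRS 5 and 5 free days, scores 2×5/2 = 5.0 or 2×5/7 = 1.43.

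At arm level, suppose both arms rate NRS 6 on headache days over 14 days and one arm has 7 free days. Zeros give 7×6/14 = 3.0 against 6.0, a difference of 3.0. Headache days only gives 6.0 against 6.0, a difference of 0.

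**2. Which divisor the text prints.**

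- The divisor in the formula is the number of days, not of headache days or persistent days.
- The diary is filled in every evening, so a headache-free day is still a diary day. The scale runs from 0, and the numerical pain rating scale in Section 9.8 begins at absence of pain, so such a day has a natural score of 0.
- The primary outcome is named for the daily headache, not the persistent headache.
- Part A has patients keep rating average intensity once headache is sporadic, and its closing sentence separates whether persistent headache lingers from the average intensity of daily headache. A persistent-days-only score, which would leave a patient with no persistent day unscored, fits this poorly.

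Carrying the formula to sporadic periods therefore gives the column with free days = 0. The dropped-days column and the X/Y reversal need a denominator that appears nowhere in the text.

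**3. Headache hours.** The supplied text does not settle whether the NRS item is a 24-hour average or intensity while headache is present.

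- If it is a 24-hour average, 6 hours at NRS 5 is 6×5/24 = 1.25, and hours already act on the primary score. Multiplying by hours again would give 1.25×6/24 = 0.31, a double count.
- If it is intensity while present, a fall from 24 to 6 hours at NRS 5 leaves the score at 5.

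Hours are thus lost to the primary score only under the second reading. Even then, five 6-hour days and two free days, 5×6/7 = 4.29 h/day against 24, would be data recorded but given no formal test.

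**4. Aim 1 against Hypothesis #1.** The hypothesis joins duration to frequency of exacerbation, and the composite multiplies exacerbation duration, frequency and intensity. On that reading, duration has its outcome.

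**5. Part A against Section 9.8.** The log entry in 9.8 is a short summary with the form attached. It is silent on hours and does not deny them, so the two places do not conflict.

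**The case for a change.** The strongest case for a change is that the choice touches the primary outcome, falls mainly on patients who improve, and is not written down. The scoring sentence is limited to persistent headache; the zero and the denominator are inferred; and the biostatistician knows the allocation. A single paragraph would remove the doubt, and Aim 1 is not limited to exacerbations.

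Much of this is true. The zero and the denominator are not stated, and the arithmetic on divergent readings is correct. What does not stand is the suggestion that the readings are equally open: the alternatives each require reading something into the text that it does not say. The supplied text is also incomplete here. Part A refers to Appendix 6b for assessment samples and cites earlier studies on the sporadic-headache sentences, and Section 9.8 says the log is attached. The item wording and scoring would naturally sit in those sources.

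On duration, a primary outcome based on intensity is an endpoint choice. A separate hours outcome may be of interest, but it would enlarge the multiplicity family in a trial whose COVID-19 section shows follow-up already under way, and the hours may not have been captured for every patient. The M-VAS, rated for the whole between-visit period and kept as a back-up for missing data, the headache impact test and the NSI headache items give further views of the same change.

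**Conclusion.** The omission is real but is one that analysts fill sensibly: a headache-free day scores 0, an uncompleted day is missing, and the denominator is all completed days, alike in both arms. The gaps of 0.71 to 2.14 NRS points in the illustrative week measure the distance to a rule the text does not support; they are not an expected error. This rests on the diary being kept every evening as described, on the printed divisor being applied as written, and on nothing in the unsupplied log or appendix saying otherwise.

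One practical consequence belongs in the analyst's working: a wholly headache-free period scores 0, so a log transform, which the plan offers only as an example and only if needed, would require an offset or another transformation. The hours outcome is an optional addition, and the text does not support a flat statement that hours enter no listed outcome. No change to the plan is called for.

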### **Statistical Analysis:**

Data will be analyzed using mixed effects model [12; 27; 35]. This approach provides more information and therefore, more power compared to cross-sectional analyses, which focus on the analysis of one summary index, or more traditional analytic approaches such as a change score, end-point or repeated measures analysis of variance. In this approach, the repeated measures over time for each individual subject form a trajectory that can be described by a relatively simple model with a few parameters, such as intercept (baseline value) and slope (rate of change). With repeated measures, repeated observations within subjects are potentially correlated for any impact on the resulting tests of significance [34]. When this within subject correlation is properly incorporated, the repeated measures analysis takes full advantage of all information obtained from each subject, thereby greatly increasing the statistical power over methods that compare treatments cross-sectionally [23]. This approach can model for the differential patterns over the repeated assessments, instead of the totals at one point. As a result, this analytical approach increases the reliability of the measurement of response (since the slope combines repeated measures, which cancel much of the error of measurement), and will increase the protection against the major effects of missing data. In addition, the influence of missing data is reduced since it maximizes the number of subjects by allowing the inclusion of subjects with missing data, dropouts or those who are terminated early in the study without relying on data imputation procedures. The investigators will use pattern-mixture models to assess if there is any bias due to drop out or missing data. These will result in

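### If intensity is averaged unweighted over episodes, the debilitating-headache composite can rise when a short, milder episode disappears; its value for an episode-free period is not stated

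*Combined protocol and SAP*

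**What the plan says.** Section 9, part A (Headache assessment), asks patients to "report the duration and intensity of any debilitating headache exacerbations, which completely incapacitate their daily functions" in a daily diary. The composite for each between-visit period is then formed by "multiplying the average duration (hours/episode) of the headache exacerbation by the average frequency (episodes per day) and the average intensity (NRS". Intensity is on a numerical scale from 0 to 10.

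Two details are absent. The text gives no weighting or denominator for the intensity average, although for persistent headache in the same part it does give one: "sum of headache NRS scores/number of days". It also gives no score for a period without exacerbations.

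The section on data management, analysis and power calculations gives the composite its role: "Secondary outcome: Debilitating Headache Composite Score (B1, B2, B3, B4, B5, B6". It falls under Hypothesis 1, which Section 6 words as "Active rTMS at LMC provides significantly more reduction in headache intensity, duration and frequency of exacerbation than sham rTMS". The analysis is a mixed effects model, credited with "allowing the inclusion of subjects with missing data, dropouts or those who are terminated early in the study without relying on data imputation procedures". Transformation of skewed outcomes is allowed, with the log as the example. None of these passages says what happens to an episode-free period.

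**The concern.** A burden score should not go up when a patient loses an episode and nothing else gets worse. A product of separate averages does not guarantee this. Losing a short, mild episode takes little off the total hours but raises the mean intensity of the episodes that remain.

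A patient with no episodes at all has no mean duration and no mean intensity, so the formula returns nothing for the best possible result. Such periods are foreseeable. The inclusion criteria set a threshold for persistent headache but require no exacerbation, so even the pre-treatment period may be empty. The first post-treatment visits are weekly, so some diary periods are short. The background section also reports that exacerbation frequency and duration fell by more than half in the investigators' own survey.

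The composite is the only listed outcome built from exacerbation episodes. The part of Hypothesis 1 about their duration and frequency therefore rests on it, and a single product cannot show which component moved.

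**Working it through.** The plan states no figure that depends on this score, so there is none to reproduce. The check is on the definition.

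**Algebra.** Let a period of T days hold n episodes with durations d (hours) and intensities i (NRS). On the unweighted reading,

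C = (Σd/n) x (n/T) x (Σi/n) = (Σd/T) x mean(i).

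The additive alternative is B = Σ(d x i)/T. Dropping an episode with positive duration and intensity always lowers B. It raises C when the proportional rise in mean intensity exceeds the ratio of old to new total hours.

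**A reversal, T = 7** (invented episodes). Before: 8 h at NRS 9 and 1 h at NRS 5. After: the 1 h episode is gone.
- C before = 4.5 x 2/7 x 7 = 9.00
- C after = 8 x 1/7 x 9 = 10.29, a rise of 14.3%
- B before = (72 + 5)/7 = 11.00; B after = 72/7 = 10.29
- Condition: mean intensity rises by 9/7 = 1.29; hours ratio is 9/8 = 1.13, so C rises

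If the remaining episode also eases to 7.5 h at NRS 8.8, C after = 66/7 = 9.43, still 4.8% above 9.00.

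With high ratings only (4 h at NRS 10 and 0.5 h at NRS 7, the short one lost), C goes from 2.25 x 2/7 x 8.5 = 5.46 to 40/7 = 5.71, a rise of 4.6%. B falls from (40 + 3.5)/7 = 6.21 to 5.71.

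**Cases without reversal.**
- 4 h at NRS 9 and 2 h at NRS 7 over 7 days, the second lost: C = 3 x 2/7 x 8 = 6.86, then 36/7 = 5.14, a 25% fall.
- 10 h at NRS 10 plus three 1 h episodes, all three lost, T = 7. With the short episodes at NRS 5, C goes from 3.25 x 4/7 x 6.25 = 11.6 to 100/7 = 14.3. With them at NRS 7, it goes from 3.25 x 4/7 x 7.75 = 14.39 to 14.29, and the reversal has gone.
- Every episode persists and only shortens or eases: n is fixed, neither Σd nor mean(i) rises and at least one falls, so C must fall. Example: 8 h at NRS 9 with the second episode easing from 1 h at NRS 5 to 0.5 h at NRS 4 gives 9.00, then 4.25 x 2/7 x 6.5 = 7.89.

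**How often.** The documents hold no exacerbation data, so this is a simulation on assumed inputs: 2 to 8 episodes, lognormal durations, duration-intensity correlation 0 to 0.5. The last column is the share of simulated cases in which C rises when the lowest-rated episode is removed.

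| NRS range of episodes | C rises |
|---|---|
| 1 to 10 | 34 to 55% |
| 5 to 10 | 12 to 26% |
| 7 to 10 | 4 to 12% |

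Removing a randomly chosen episode raises C in about 1 to 17% of cases across these settings.

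**Episode-free periods.** With n = 0, Σd/n and Σi/n are both 0/0. To show what the coding can do, assume a mean score of 20 among patients with episodes in both arms, and 30% (active) against 10% (sham) episode-free.
- Coded missing: 20 - 20 = 0
- Coded 0: 20 x 0.70 - 20 x 0.90 = -4

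The second figure is -1 at 10% against 5%, and -6 at 50% against 20%.

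**The case against.** Only episodes that stop all daily function count, so ratings may cluster high, and the clearest reversals use low ratings such as NRS 5 for an incapacitating headache. This stands. It makes the reversal uncommon if ratings do cluster high, but not impossible, as the NRS 10 and 7 example shows.

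The intensity average might be duration-weighted. Then C = (Σd/T) x (Σ(d x i)/Σd) = B, and no reversal can occur. The wording does not exclude this, and the cited earlier papers and the assessment samples in the appendix are not to hand. The point is therefore tied to the unweighted reading, which is the natural one for an average listed beside duration per episode.

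For an episode-free period frequency is plainly 0, so a score of 0 is the obvious convention, and no passage says that such periods are missing. This also stands: taken alone, that gap is a clarification. It matters because zero has to be stated to be relied on, and because a plain log cannot take it.

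Hypothesis 1 has other outcomes. Average daily headache, the primary, covers intensity, and the symptom inventory (NSI) is described as covering headache pattern. None of the listed alternatives is derived from the duration and frequency of individual exacerbations.

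A reader might go further and infer that if active treatment first removes the shorter, milder episodes, the score will move the wrong way, so that the comparison is biased towards no benefit. The documents do not support this. The 6.86 to 5.14 example is exactly such a removal and the score falls, and nothing in the documents shows which mixes of episodes the patients have.

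**Conclusion.** On the unweighted reading, the composite can record the loss of an episode as a worsening (9.00 to 10.29 in the simplest example), and it has no stated value for a period with no episodes. Both follow from the definition as written. How often the reversal would occur, and which way it would push the arm comparison, are unknown; the simulated frequencies and the 0 against -4 contrast rest on assumed inputs.

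The reach is limited to one secondary outcome. A reader might infer that the primary result or the sample size of 128 is in doubt; neither uses this score. The point is still worth acting on, because no other listed outcome is built from exacerbation episodes and a better-behaved score should be available from the same diary.

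**What to change.** Before unblinding, and documented as an amendment:

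1. Score each diary period as the sum over episodes of duration (hours) x NRS, divided by completed diary days.
2. Score a completed episode-free period as 0, and keep this distinct from a diary that was not filled in.
3. Use an analysis or transformation that admits zeros, not a plain log.
4. Report episodes per day, hours per day and mean episode intensity descriptively by arm, so that the separate claims in Hypothesis 1 can be read. The summed score cannot show this by itself either.
5. Keep the product-of-averages score as a sensitivity analysis, with its intensity weighting and its episode-free value stated.

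The cost is a short scoring paragraph and a changed derivation program. The main score will no longer be identical to the one in the cited earlier work, which item 5 covers. The COVID-19 text shows that subjects are already in follow-up, so this redefines a secondary outcome in mid-trial, and its date and the blinded status of those making it should be recorded. The sum also needs the diary to pair duration and intensity for each episode, which the protocol implies but does not state; check this first. If they are not paired, state the weighting and the zero rule for the present score and report the components.
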